4.0 Purpose

The SAP describes the statistical methods to be used during the reporting and analyses of data collected under CureVac AG Protocol CV-NCOV-004 (HERALD).

5.0 Scope

The SAP outlines the following:

- Trial Objectives
- Trial Design
- Trial Endpoints and Assessments
- Analysis Sets
- Conventions and Definitions
- Applicable Trial Definitions
- Statistical Methods

6.0 Introduction

The SAP describes the statistical methods to be used during the reporting and analyses of data collected under CureVac AG Protocol CV-NCOV-004.

The SAP should be read in conjunction with the trial protocol version 4.0 dated 25-NOV-2021 and Case Report Form (CRF) 6.0 dated 22-Oct-2021.

This SAP describes the statistical methods used for the final primary efficacy analysis (when at least 160 cases have been accrued), and a 1-year follow-up analysis (on all data up to Day 393 visit), as well as the planned interim analyses (when at least 56 and 111 cases have been accrued).

Changes performed on the SAP after approval of version 1.0 are tracked in the SAP Change Log.

Each version of the SAP requires approval by the Sponsor.

The SAP final versions 1.0 and 2.0 were finalized and approved prior to the first interim analysis (IA) (the IA when at least 56 cases had been accrued).

The SAP final versions 3.0 and 4.0 were finalized and approved prior to unblinding and the final primary efficacy analysis.

6.1 SAP Version 5.0: Background, Rationale and Specifics

After the final primary efficacy analysis but prior to the 1-year follow-up analysis, CureVac decided to withdraw CVnCoV from the current approval process with the European Medicines Agency (EMA). Due to availability of Authorized Vaccines (AVs) for preventing Coronavirus Disease 2019 (COVID-19) the trial was converted to an open-label design with the focus on safety monitoring. Protocol version 4.0 was issued in that context.

The main purpose of the protocol amendment is:

- To unblind all remaining blinded subjects and inform them of the treatment received.
- To monitor safety of the following subjects remaining in the open-label phase after unblinding:
 - Subjects who had received CVnCoV and received/will receive an AV through their national vaccination program.
 - Subjects who had received CVnCoV and continue follow-up in the trial as initially planned, without receiving an AV.

SAP version 5.0 is mainly required to cover the changes between protocol version 3.0 and 4.0

On agreement with the Sponsor SAP version 5.0 is created before approval of protocol version 4.0 by all authorities. In case protocol version 4.0 is rejected by any authority, protocol version 3.0 automatically applies. Therefore SAP version 5.0 provides separate wording for protocol version 4.0 changes that is conditional to the protocol version 4.0 being accepted. This prevents the requirement of a new SAP version in case protocol version 4.0 is rejected.

For ease of reading the condition of protocol 4.0 being fully approved is referred to as "Scenario A" (A referring to "Approved") and the condition of protocol 4.0 being rejected/not approved by at least one of the authorities is referred to as "Scenario R" (R referring to "Rejected"). If only one of these 2 scenarios is mentioned this implies that the other scenario is reflected by the remaining text without any alterations required. If none of these scenarios is mentioned the related wording is applicable for the blinded phase under Scenario A and to the whole study under Scenario R. Also, "in the blinded study phase" might be used without mentioning that this is conditional to Scenario A. Under Scenario A "in the blinded study phase" applies to the blinded study phase. Under Scenario R "in the blinded study phase" applies to the whole study.

Important note: Some main stakeholders from the combined Sponsor and Contract Research Organization (CRO) study team, amongst others the full CRO study team and the Sponsor statistician, had already been unblinded at the time of the final primary efficacy analysis. The remaining Sponsor study team was unblinded on 25-Nov-21. As a consequence, the SAP version 5.0 is created and approved by an unblinded authorship/approval team.

6.2 Changes / Intended Divergence from Protocol Version 4.0

- The following selected Safety summary tables to be provided by gender:
 - Overall Summary of Unsolicited Adverse Events Occurring on the Day of Vaccination and the following 28 Days after any Dose
 - Overall Summary of Unsolicited Adverse Events Occurring on the Day of Vaccination and the following 28 Days after Dose 1
 - Overall Summary of Unsolicited Adverse Events Occurring on the Day of Vaccination and the following 28 Days after Dose 2
 - Summary of Solicited Adverse Events Overall and by Maximum Grade Occurring on the Day of Vaccination and the following 7 Days after any Dose
 - Summary of Solicited Adverse Events Overall and by Maximum Grade Occurring on the Day of Vaccination and the following 7 Days after Dose 1
 - Summary of Solicited Adverse Events Overall and by Maximum Grade Occurring on the Day of Vaccination and the following 7 Days after Dose 2
- The EAS excludes subjects who were unblinded prior to 15 days after the second vaccination or received an AV prior to 15 days after the second vaccination.
- Additional population set (EASU) are introduced to account for subjects receiving an AV during the course of the trial.
- The following deletion was performed on the definition of an exploratory safety endpoint:
 "Only for Cohort A: CVnCoV-AV: Occurrence of AEs leading to **AV withdrawal or** trial discontinuation after the first dose with an AV in the open-label phase until EOT."
- Although not clearly determined in the protocol, no efficacy or reactogenicity analyses are performed at EOT analysis. Therefore some endpoints or parts of endpoints are not analyzed in this study. For reactogenicity, these are specified in Appendix 6, for efficacy these are:
 - All analyses on the PPE.
 - Occurrence of virologically-confirmed (RT-PCR positive) SARS-CoV-2 infection, with or without symptoms.

- Occurrence of first episodes of virologically-confirmed (RT-PCR positive) cases of COVID-19 caused by individual VOCs.
- Occurrence of supplemental oxygenation, mechanical ventilation, hospitalization and death due to COVID-19 at any time after the first trial vaccination in naïve subjects
- Occurrence of death due to any cause at any time after the first trial vaccination in naïve subjects.
- Occurrence of first episodes of virologically-confirmed (RT-PCR positive) cases of COVID-19 of any severity in all subjects, regardless of their baseline serostatus.
- Occurrence of second episodes of virologically-confirmed (RT-PCR positive) cases of COVID-19 of any severity in subjects who had a first episode of a virologically-confirmed (RT-PCR positive) case of COVID-19 of any severity meeting the case definition for the primary efficacy analysis.

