3.1.4 HERALD Phase 2b/3 Results

The HERALD final efficacy analysis on 25,062 subjects meeting the inclusion criteria for the primary analysis, including 228 confirmed adjudicated COVID-19 cases, has demonstrated:

- An overall CVnCoV vaccine efficacy (VE) of 48% (p=0.01600, 95.826% CI 31.0-61.4%) for all age groups against COVID-19 of any severity, including single non-respiratory mild symptoms.
- Significant protection was also shown among subjects in the age group of 18 to 60 years, with an efficacy of 52.5% (95% CI 36.2-64.8%) against disease of any severity and across the 15 identified strains; protection against moderate to severe disease was 77% (95% CI 51.8-90.4%).
- In subjects over 60 years (21 cases, 9% of the analyzed COVID-19 cases), the available data did not allow a statistically significant determination of efficacy. Therefore, CureVac reassessed the benefit/risk by age group and advised the investigators to discuss administration of an AV to trial subjects ≥ 60 years.
- Overall, the data confirm the favorable safety profile of CVnCoV.

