10.3.5.2 Secondary Efficacy Endpoints Analyses

Statistical testing of the 3 key secondary efficacy endpoints will be performed according to the conditional hierarchical testing procedure using the order defined in the objective/endpoints sections. Consequently:

- Efficacy of CVnCoV in regard to moderate and severe cases will be demonstrated only if there is successful demonstration of the primary efficacy objective.
- Efficacy of CVnCoV in regard to severe cases will be demonstrated only if there is successful demonstration of the primary efficacy objective and the key secondary objective on moderate and severe cases.
- Efficacy of CVnCoV in regard to (RT-PCR positive) cases of "wild type" (i.e., WT/D614G lineages A.1/B.1 without VOC B.1.1.7 [Alpha], B.1.351 [Beta], B.1.429 [Epsilon]) and "UK" (B.1.1.7 [Alpha]) will be demonstrated only if there is successful demonstration of the primary efficacy objective and the key secondary objective on moderate and severe cases and severe cases.

Otherwise, these endpoints will be analyzed as exploratory endpoints without success criteria testing.

To assess the efficacy in the prevention of "wild type" (i.e., WT/D614G lineages A.1/B.1 without VOC B.1.1.7 [Alpha], B.1.351 [Beta], B.1.429 [Epsilon]) and "UK" (B.1.1.7 [Alpha]) cases, moderate to severe, severe disease and asymptomatic infections, similar analyses to those performed on the primary efficacy endpoint will be performed. The efficacy will be demonstrated if the lower limit of the exact 2-sided 95% CI of VE is above 30% for "wild type" (i.e., WT/D614G lineages A.1/B.1 without VOC B.1.1.7 [Alpha], B.1.351 [Beta], B.1.429 [Epsilon]) and "UK" (B.1.1.7 [Alpha]) cases, 20% for moderate to severe disease, 10% for severe disease and above 0% for asymptomatic infections.

Other secondary efficacy endpoints will be analyzed similarly to the primary efficacy endpoint but no formal testing will be performed for those endpoints. For efficacy after the first dose, the time to first-occurrence of virologically-confirmed COVID-19 (date of symptom onset) will start after the first vaccination. The BoD will be analyzed using 2 different scoring systems. Both BoD scoring systems place more weight on efficacy against severe COVID-19 or severe disease as reflected by hospitalization or death. In addition, VE and associated CI will be calculated for each of the BoD categories.

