9.6.9 Summary of Analysis Sets to be Used per Analysis

Table 3Table 4 and Table 4Error! Reference source not found. below provide an overview on the Analysis Sets used for the analyses of each endpoint.

Table 3: Summary of Analysis Sets to be Used per Analysis - Efficacy Endpoints

ENDPOINT TYPE	ENDPOINT SHORT DESCRIPTION	ANALYSIS SET
PRIMARY EFFICACY ENDPOINT	First episodes of COVID-19 cases.	EAS
	First episodes of moderate to severe COVID-19 cases.	EAS
KEY SECONDARY EFFICACY ENDPOINT	First episodes of severe COVID-19 cases.	EAS
	“Wild type” and “Alpha” SARS-CoV-2 strains	EAS
	First episodes of COVID-19 cases in subjects ≥ 61 years of age	EAS*
OTHER SECONDARY EFFICACY ENDPOINT	First episodes of SARS-CoV-2 infection, with or without symptoms.	EAS
	BoD Scores	EAS
	First episodes of COVID-19 cases with symptom onset at any time after the first trial vaccination	SAS [#]
	Severity assessment of first episodes of COVID-19 cases	EAS
	Any strain COVID-19	EAS
	Supplemental oxygenation, mechanical ventilation, hospitalization, death (cases ≥ 15 days after second vaccination)	EAS
EXPLORATORY EFFICACY ENDPOINT	Supplemental oxygenation, mechanical ventilation, hospitalization, death (cases after first dose)	SAS
	First episodes of COVID-19 cases with symptom onset ≥ 15 days after second vaccination, regardless of baseline serostatus	SAS ^{\$}
	First episodes of COVID-19 cases with symptom onset at any time after the first vaccination, regardless of baseline serostatus	SAS

ENDPOINT TYPE	ENDPOINT SHORT DESCRIPTION	ANALYSIS SET
	Second episodes of COVID-19 cases	EAS

* RESTRICTED TO SUBJECTS ≥ 61 YEARS OF AGE

RESTRICTED TO SUBJECTS WITH NEGATIVE BASELINE SEROSTATUS

\$ RESTRICTED TO SUBJECTS WHO RECEIVED BOTH DOSES AS RANDOMIZED, DID NOT DEVELOP A COVID-19 CASE OR DISCONTINUED TRIAL PRIOR TO 15 DAYS AFTER SECOND VACCINATION

Table 4: Summary of Analysis Sets to be Used per Analysis - Safety and Immunogenicity Endpoints

ENDPOINT TYPE	ENDPOINT SHORT DESCRIPTION	ANALYSIS SET
	Occurrence, intensity and relationship of medically-attended AEs	SAS
	Occurrence, intensity and relationship of SAEs and AESIs	SAS
	Occurrence of fatal SAEs	SAS
PRIMARY SAFETY ENDPOINT^{\$}	Occurrence, intensity and duration of solicited local AEs	SASsol
	Occurrence, intensity and duration of solicited systemic AEs	SASsol
	Occurrence, intensity and relationship of unsolicited AEs	SAS 2
	Occurrence of AEs leading to vaccine withdrawal or trial discontinuation	SAS

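### SAP v5.0, written unblinded, drops the protocol's secondary endpoint of RT-PCR-confirmed infection with or without symptoms and gives no endpoint-specific reason

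*SAP*

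**What the plan says.** **Protocol v4.0** (25 November 2021)
- Section 4.2.2 lists RT-PCR-confirmed infection, symptomatic or not, under other secondary efficacy endpoints. Onset (if symptomatic) or the positive test (if asymptomatic) must fall at least 15 days after dose 2.
- Section 4.3 gives it an estimand: VE as one minus the ratio of attack rates, in EAS subjects. Table 9 names the EAS as its primary population.
- Section 10.3.5.2 fixes its status: "Other secondary efficacy endpoints will be analyzed similarly to the primary efficacy endpoint but no formal testing will be performed for those endpoints".
- Section 3.1.4 already reports the primary result: "An overall CVnCoV vaccine efficacy (VE) of 48% (p=0.01600, 95.826% CI 31.0-61.4%) for all age groups".

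**SAP v5.0** (10 March 2022)
- Section 6.1 gives the timing, "After the final primary efficacy analysis but prior to the 1-year follow-up analysis, CureVac decided to withdraw CVnCoV", and says that "the SAP version 5.0 is created and approved by an unblinded authorship/approval team".
- Section 6.2 lists outcomes that will not be analysed, because no efficacy or reactogenicity analyses are run at end of trial (EOT). The list includes "Occurrence of virologically-confirmed (RT-PCR positive) SARS-CoV-2 infection, with or without symptoms" and also the exploratory endpoint of first "cases of COVID-19 of any severity in all subjects, regardless of their baseline serostatus".
- The Change History entry for v5.0 records both removals.
- Sections 7.2.2, 9.2.2 and 12.6.3.3 no longer contain the infection endpoint. Table 3 in Section 9.6.9 still does: "First episodes of SARS-CoV-2 infection, with or without symptoms", on the EAS.

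**The concern.** A pre-specified secondary outcome was taken out of the analysis plan by people who knew the treatment codes and the primary result. The stated reason concerns the EOT analysis, whereas this endpoint belongs to the efficacy data set closed in June 2021. A reader of the trial report would expect VE against infection, because the governing protocol promises it, and would not find it.

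What is at stake is the credibility of the set of reported efficacy outcomes, not any confirmatory claim. Protocol v4.0 had already dropped seroconversion to N protein. With RT-PCR infection gone as well, no VE analysis against infection in any form remains: the burden-of-disease scores give asymptomatic infection a zero, and every other efficacy endpoint requires symptomatic disease or a clinical outcome of it, apart from all-cause death.

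**Working it through.** The point rests on comparing passages. The arithmetic only marks what is and is not affected.

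**1. Order of events.** Efficacy cut-off and end of adjudication: 18-Jun-2021 (SAP 10.7.6). Protocol v4.0: 25-Nov-2021, with the primary result in its Section 3.1.4. SAP v5.0: 10-Mar-2022. The protocol therefore kept the endpoint with the result known, and the SAP removed it about three and a half months later.

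**2. How a comparable removal was handled.** Protocol Appendix 11 removes N-protein seroconversion with a reason specific to it: the result is no longer relevant for CVnCoV now that many subjects have received an authorised vaccine. The RT-PCR infection endpoint survived that same amendment. SAP 6.2 then removes it under the general EOT statement, with no reason of its own.

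**3. Does the EOT reason cover this endpoint?**
- SAP 10.8 defines asymptomatic cases and their onset date (the positive central RT-PCR).
- SAP 10.7.6 places asymptomatic infections under the adjudication committee, whose work ended at the 18-Jun-2021 cut.
- SAP 9.6.2 uses asymptomatic infection before day 15 after dose 2 to exclude subjects from the EASU, and hence from the EAS. The plan thus uses early asymptomatic infections to define the population but reports nothing on later ones.
- SAP 12.6.3.3 provides the other secondary endpoints it lists at the interims and at the primary efficacy delivery. Nothing says why infection was not among them.
- The EOT rule is not absolute: SAP 12.6.1 allows primary and key secondary outputs to be re-run with the EOT analysis after the unblinding dates at site AR009 were corrected.

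No new data were needed, so the reason does not explain the omission.

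**4. Consistency within the SAP.** Sections 6.2, 7.2.2, 9.2.2 and 12.6.3.3 say the endpoint is gone, and Table 3 says it is analysed on the EAS. Table 11 has no row for it but keeps a footnote on asymptomatic subjects.

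**5. Effect on the design figures.** For the primary test with equal follow-up:
- null share of cases = 0.7/1.7 = 0.4118; alternative = 0.4/1.4 = 0.2857, both as stated in the plan;
- exact one-sided p for 53 of 160 cases = 0.0224, below 0.02281; for 54 of 160 it is 0.0327, so the stated cut-off is right;
- power at the final look alone = 91.2%, against the stated 90%.

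The key secondary powers also reproduce: 91.5% (53 cases), 81.5% and 91.0% (32 cases), 90.7% (80 cases). The infection endpoint enters none of these, so restoring it changes none of them.

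**6. Events for the missing analysis.** Every primary case is also an RT-PCR-confirmed infection in the same window. Protocol 3.1.4 reports 228 such cases, so the infection endpoint has 228 + k subjects with an event, where k is the number with only asymptomatic confirmed infection. The documents do not give k.

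**7. The exploratory all-serostatus VE.** SAP 12.6.3.3 keeps VE from dose 1 on the SAS, restricted to baseline-seronegative subjects. The SAS needs one dose, and SAP 10.6.1 requires only baseline seronegativity for this endpoint. On the protocol's assumption of about 5% baseline seropositivity, it covers about 100% − 5% = 95% of vaccinated subjects.

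**The case against.** The case on the other side is substantial.

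- *The removal is open.* Section 6.2 and the Change History both state it, and Section 6.1 discloses the unblinded authorship. The cut is also broad: it takes in the per-protocol efficacy set, individual variants, second episodes and many reactogenicity tables, and it follows withdrawal from EMA review and the move to safety follow-up. A reader might infer selective reporting driven by the infection result. The documents do not support that: nothing shows that this result had been seen or that it guided the choice. The superseded SAP v4.0, which would show when the output was scheduled, is not available. This stands in full.
- *The endpoint carries no formal test and may add little.* Protocol 9.2.2 rules out active surveillance for asymptomatic infection, so such cases come in mainly through tests taken outside the site and reported by the subject. If k is small, the estimate will sit close to the primary VE. This limits the value of the table but does not justify omitting a protocol endpoint.
- *The serostatus-free analysis.* A reader might infer that dropping it removes the only check on selection into the EAS. It does not. The retained dose-1 analysis already lifts the dose-2, Day 43 and early-case exclusions; the dropped one would add only baseline-seropositive subjects, and it is exploratory. Nor does comparing the 25,062 analysed subjects with 36,500 planned (68.7%, so about 31% outside) measure the effect of either deletion. The denominator is planned enrolment, the SAP's EAS also excludes early unblinding and early receipt of an authorised vaccine, and vaccinated baseline-seronegative subjects outside the EAS are in the dose-1 analysis.

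**Conclusion.** The point holds for one endpoint. SAP v5.0 deletes a protocol other secondary efficacy outcome after unblinding, for a reason that does not apply to it, while its own Table 3 still plans the analysis. It should be corrected, but it is not a threat to the trial's conclusions: no alpha, no power figure and no primary or key secondary result depends on it.

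The effect on the reported evidence cannot be quantified, because the number of asymptomatic confirmed infections is not given. The judgement assumes that the adjudicated asymptomatic cases up to 18-Jun-2021 are in the database, as SAP 10.7.6 implies. It implies nothing about intent. The loss of the exploratory all-serostatus VE is a lesser matter, affecting about 5% of vaccinated subjects on the protocol's assumption.

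**What to change.** 1. Delete the infection endpoint from the list in SAP 6.2. Restore it in Sections 7.2.2, 9.2.2 and 12.6.3.3, in the estimand table of Section 9.5, and as a row in Table 11. That row should start 15 days after dose 2, take symptom onset or (if asymptomatic) the positive central RT-PCR as the event date, and use the censoring of the primary endpoint.
2. Report VE with an exact 95% CI and no p-value on the EAS at the 18-Jun-2021 cut. State that asymptomatic infection was passively ascertained, that the analysis was restored after unblinding, and which AR009 unblinding dates were used.
3. Protocol 10.3.5.2 sets a lower-limit criterion above 0% for asymptomatic infections but rules out formal testing of other secondary endpoints. Reconcile the two and treat this analysis as estimation only.
4. Optionally, run the exploratory VE regardless of baseline serostatus on the same cut, on the SAS and in both windows as Table 3 specifies. Its Table 11 rows are still there, through the footnote marked +.
5. If the sponsor prefers to leave the infection endpoint out, give a reason specific to it and label the omission in the report as a post-unblinding decision. Reconcile Table 3 with Section 6.2 in any case.

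The cost is one estimation-only table on data already collected and adjudicated (a little more with the optional analysis), plus text edits to the SAP.

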7.0 Trial Objectives

Scenario A: For those sites where the protocol was accepted the objectives mentioned in Sections 7.1 – 7.3 are to be considered the objectives of the blinded study phase objectives and Section 7.4 becomes effective.

Scenario R: For those sites where the protocol was not accepted, the objectives mentioned in Sections 7.1 – 7.3 are considered the overall study objectives and Section 7.4 becomes redundant.

7.1 Primary Objectives:

7.1.1 Primary Efficacy Objective

- To demonstrate the efficacy of a 2-dose schedule of CVnCoV in the prevention of first episodes of virologically-confirmed cases of COVID-19 of any severity in Severe Acute Respiratory Syndrome Coronavirus 2 (SARS-CoV-2) naïve subjects.

7.1.2 Primary Safety Objectives

- To evaluate the safety of CVnCoV administered as a 2-dose schedule to subjects 18 years of age and older.
- To evaluate the reactogenicity of CVnCoV administered as a 2-dose schedule to subjects 18 years of age and older participating in Phase 2b of the trial.

7.2 Secondary Objectives:

7.2.1 Key Secondary Efficacy Objectives

- To demonstrate the efficacy of a 2-dose schedule of CVnCoV in the prevention of first episodes of virologically-confirmed moderate to severe cases of COVID-19 in SARS-CoV-2 naïve subjects.
- To demonstrate the efficacy of a 2-dose schedule of CVnCoV in the prevention of first episodes of virologically-confirmed severe cases of COVID-19 in SARS-CoV-2 naïve subjects.
- To demonstrate the efficacy of a 2-dose schedule of CVnCoV in the prevention of first episodes of virologically-confirmed cases of COVID-19 of any severity caused by “wild type” and “Alpha” SARS-CoV 2 strains in SARS-CoV 2 naïve subjects.

